#### SECTION 1A. RESEARCH STUDY OVERVIEW

#### **Subsection 1A.1 Overview & Introduction**

This three-year study will be a mixed-method, open-label cluster randomized clinical trial to test the benefit of the adapted mindful self-compassion intervention (MSC) at improving primary (PTSD, substance use) and secondary outcomes (depression, anxiety, helplessness, loneliness) among a sample of women experiencing homelessness (WEH) with PTSD/SUD residing in a residential drug treatment site (RDTS). An exploratory aim will be to elucidate mechanisms of treatment-response and maintenance or remission of symptoms.

Phase 1 of this three-year study was completed in December 2023. In Phase 1, a Community Advisory Board (CAB) was created, with women from the RDTS as well as site staff (including clinicians and substance use counselors). The CAB and the UCLA research team jointly created a semi-structured interview guide that was used with four focus groups (total N=27) of trauma-exposed WEH living at the RDTS. The participants completed acceptability and feasibility questionnaires and provided feedback on program design and administration. These suggestions were brought to the CAB and together the study design was finalized accordingly.

Phase II of this study will begin in Winter/Spring 2024. This will be a clinical trial comparing the MSC intervention to treatment as usual (TAU).

### **Subsection 1A.2 Research Team and Responsibilities**

### Principal Investigator (PI): [name] [name]

Oversees scientific and administrative direction of the project. Makes executive decisions regarding the implementation of the study, data entry and data analysis approaches, and interpretation of study findings. She will train the research staff and assistants to perform content. [name] will select all questionnaires and oversee the design, implementation, and evaluation of the MSC and treatment as usual (TAU) control. [name] takes final responsibility for the integrity of the data and the accuracy of the data analysis. She will also be responsible for tracking and reporting any adverse events that occur.

### **Graduate Student Researchers (GSRs):**

First line contact for RAs, responsible for RA scheduling, delegates lab responsibilities to other RAs, oversees RAs on site at the RDTS, keeps track of supplies, reimbursements, and participant compensation, assists with research tasks including qualitative data group coding, setting up REDCap, and writing papers.

### **Undergraduate Research Assistants (RAs):**

Assist with delegated lab tasks, including ordering supplies, screening and interviewing study participants at the RDTS, and inputting data into REDCap.

### **Subsection 1A.4 Phase II Timeline**

Table 3. Study Timeline												
Year 1												
Month	1	2	3	4	5	6	7	8	9	10	11	12
Stud	y st	art up	Phase 1	: CAE	3 & FC	GS		Phase	II: Col	nort 1	Coho	rt 2
Year 2												
Month	1	2	3	4	5	6	7	8	9	10	11	12
		Cohor	t 3		Cohor	t 4		Coho	t 5		Coho	ıt 6
Year 3												
3.5 4	_											10
Month	1	2	3	4	5	6	7	8	9	10	11	12
Month	1	2 Cohor		•	5 Cohor		7	_	-	10 Dissemi		12

#### 6. BASIC DEFINITIONS

**Mindful Self Compassion (MSC):** is a mind-body integrative health intervention that utilizes meditations, other contemplative practices, home practices, and experiential exercises (including group discussions) to increase SC. To increase feasibility of MSC for use in the RDTS, we will adapt MSC to 7 sessions (6 weekly sessions in alignment with the MSC short course plus the half day retreat included in the full course to facilitate skill consolidation).

**Post-traumatic Stress Disorder (PTSD):** PTSD is a psychological pathology characterized by re-experiencing, avoidance, negative thoughts or cognitions, hyperarousal after experiencing a traumatic event.

**Trauma:** According to the DSM-5, must involve actual or threatened death, serious injury, or sexual violence.

**Arm:** The different groups of the intervention. In this study, Arm 1 is the treatment as usual (TAU) control and Arm 2 is the MSC. Participants are assigned to one Arm or the other, by cohort).

**Cohort:** The group of people that are doing the interventions at the same time.

### Other Acronyms used in the protocol:

**WEH:** women experiencing homelessness

**SUD:** substance use disorder

**TAU:** treatment as usual control group **RDTS:** residential drug treatment site

#### SECTION 1B. INTRODUCTION TO PTSD AND MSC

### **Subsection 1B.1 PTSD Basics**

### **PTSD**

PTSD occurs as the result of direct exposure to experiencing, witnessing, or learning of an event that involves actual or threatened death or serious injury or harm to self of others (American Psychiatric Association, 2013). For a diagnosis of PTSD, symptoms must be present for at least one month prior to diagnosis and must include at least one re-experiencing symptom, one avoidance symptom, two arousal and reactivity symptoms and two cognition and mood symptoms. Re-experiencing symptoms can include flashbacks, nightmares, and invasive thoughts. Avoidance symptoms are related to an individual actively avoiding locations, thoughts,

events, or objects that are reminiscent of the trauma. Arousal and reactivity symptoms include feeling easily frightened, tense, increased anger, and having issues sleeping. Cognitive and mood symptoms include but are not limited to having trouble remembering key features of the trauma, distorted feelings, and loss of interest in previously enjoyable activities. PTSD must be diagnosed by a mental health professional, but a variety of measures have been validated for use as screens or by non-clinical for research purposes. In this study, PTSD symptoms will be measured using the PTSD Checklist for DSM-5 (PCL-5).

#### **DSM-5** Criteria for PTSD

The following text summarizes the diagnostic criteria for PTSD

**Criterion A (one required):** The person was exposed to: death, threatened death, actual or threatened serious injury, or actual or threatened sexual violence, in the following way(s):

- Direct exposure
- Witnessing the trauma
- Learning that a relative or close friend was exposed to a trauma
- Indirect exposure to aversive details of the trauma, usually in the course of professional duties (e.g., first responders, medics)

**Criterion B (one required):** The traumatic event is persistently re-experienced, in the following way(s):

- Unwanted upsetting memories
- Nightmares
- Flashbacks
- Emotional distress after exposure to traumatic reminders
- Physical reactivity after exposure to traumatic reminders

**Criterion C (one required):** Avoidance of trauma-related stimuli after the trauma, in the following way(s):

- Trauma-related thoughts or feelings
- Trauma-related reminders

Criterion D (two required): Negative thoughts or feelings that began or worsened after the trauma, in the following way(s):

- Inability to recall key features of the trauma
- Overly negative thoughts and assumptions about oneself or the world
- Exaggerated blame of self or others for causing the trauma
- Negative affect
- Decreased interest in activities
- Feeling isolated
- Difficulty experiencing positive affect

**Criterion E (two required):** Trauma-related arousal and reactivity that began or worsened after the trauma, in the following way(s):

• Irritability or aggression

- Risky or destructive behavior
- Hypervigilance
- Heightened startle reaction
- Difficulty concentrating
- Difficulty sleeping

**Criterion F (required):** Symptoms last for more than 1 month.

**Criterion G (required):** Symptoms create distress or functional impairment (e.g., social, occupational).

**Criterion H (required):** Symptoms are not due to medication, substance use, or other illness. Two specifications:

- 1. Dissociative Specification. In addition to meeting criteria for diagnosis, an individual experiences high levels of either of the following in reaction to trauma-related stimuli:
  - Depersonalization. Experience of being an outside observer of or detached from oneself (e.g., feeling as if "this is not happening to me" or one were in a dream).
  - Derealization. Experience of unreality, distance, or distortion (e.g., "things are not real").
- 2. Delayed Specification. Full diagnostic criteria are not met until at least six months after the trauma(s), although onset of symptoms may occur immediately.

### **How is PTSD Typically Treated?**

CBT, cognitive processing therapy, prolonged exposure therapy (PE), eye movement desensitization and reprocessing (EMDR), stress inoculation training, psychopharmacological treatments are all common treatments for PTSD. Cognitive behavioral therapy (CBT) often occurs once a week and works with the client to reframe thoughts surrounding the event (i.e. feelings of guilt). Similarly, in cognitive processing therapy the client recounts the event and related thoughts to a therapist and subsequently processes and learns new ways to live with the thoughts and trauma. PE takes place in eight to fifteen ninety minute sessions in which the client is taught breathing techniques to combat anxiety before making a list of avoidances and learning to face them. EMDR asks the client to watch or listen to something, such as a light flashing or sound, while concentrating on the traumatic event so that over time, the client can think about something positive while remember the trauma. Stress inoculation training focuses on how the client responds to the stress of the trauma and works to teach them methods to cope such as breathing techniques and thought stopping. Medications frequently prescribed to individuals with PTSD are SSRIs and SNRIs such as Prozac and Zoloft. We are testing whether MSC is an effective complementary treatment for PTSD. Complementary means that it will be used in addition to any other interventions used in standard treatment of PTSD.

### **Subsection 1B.2 MSC Basics**

MSC is a mind-body integrative health intervention that utilizes meditations, other contemplative practices, home practices, and experiential exercises (including group discussions) to increase SC. MSC can be done in groups of 10-25. The full program typically consists of eight sessions, approximately 2.5 hours long, and a 4-hour (half-

day) silent retreat. There are a total of 25 practices in MSC (including three core meditations, four other meditations, and 18 informal practices for daily life); all incorporate loving-kindness (e.g., self-compassion). An official MSC adaptation, the MSC short course consists of six sessions and has been increasingly used in healthcare settings.  Our prior work with WEH found that the majority of WEH completed 7/9 available sessions (6 sessions or more were considered treatment completion), with most WEH citing early discharge from RDTS as the reason for lower dose of sessions. To increase feasibility of MSC for use in RDTSs, we will aim to adapt MSC to 7 sessions (6 weekly sessions in alignment with the MSC short course plus the half day retreat included in the full course to facilitate skill consolidation). Sessions will be conducted in a group-based format: prior research found group-based formats equivalent to individual-level interventions for PTSD/SUD.

**Table 1.** Progression of the adapted 6-week MSC intervention

Table 1. Overview of Key MSC Practice by Session								
Session	Topics	Key Practices for PTSD/SUD						
Session 1 What is MSC?	Why Am I Here? How to Approach MSC Guiding Principles 3 components of SC Misgivings	"How do I treat a friend"? Physiology of SC and Criticism SC Break Informal Practice: SC Bracelets						
Session 2 Practicing SC	"Resistance & backdraft" How We Cause Ourselves Unnecessary Suffering Development of Safety & Trust Inner Ally	Affectionate Breathing Practicing Loving Kindness Soles of the Feet Mindfulness & SC in Daily life Here and Now Stone						
Session 3 Discovering Your Compassionate Voice	Self-Criticism & Safety Core Values Compassionate Conversations with Self	Meeting the Inner Critic Finding Phrases Compassionate Letter to Ourselves						
Session 4 SC & Resilience	Applying SC to Difficult Emotions Hidden Values in Suffering Emotion of Shame Described & Demystified	Core Values Exercise Living with a Vow Silver Linings						
Session 5 Meeting Difficult Emotions	Self-Forgiveness Challenging Relationships	Compassionate Friend Meeting Unmet Needs SC Break in Relationships SC with Equanimity						
Session 6 Making it Count	Integrate Positive Psychology Concepts of Savoring, Gratitude, & Self-Appreciation Tips for Maintaining Practice	Savoring Gratitude Self-Appreciation						
" Living Deeply Retreat "	Half-day Retreat Conducted between Sessions 5 & 6	Soften Soothe Allow Affectionate Breathing Compassionate Movement						

#### **SECTION 2. INTERVENTION DELIVERY**

#### **Subsection 2.1 - Phase II Overview**

In Phase II, we will assess the benefit of MSC to produce improvements in primary (PTSD, SUD) and secondary outcomes (depression, anxiety, hopelessness, loneliness) compared to Treatment as Usual (TAU) and to explore mechanisms of symptom change over time. We will implement an open-label cluster randomized clinical trial of an adapted MSC course for PTSD/SUD with WEH (N=202), randomized to MSC (n=101) or TAU (n=101). Women will be recruited from Prototypes, a HealthRIGHT 360 RDTS. Inclusion criteria will be: 1) woman age 18 and over; 2) probable PTSD as judged by the PCL-5 (score of 31 or higher, indicated as having optimal signal detection); 3) no cognitive impairment according to a score of < 10 on the Short-Blessed Test; 4) experienced homelessness in the past 6 months or prior to incarceration ("spent night in public or private shelter or on the street"); and 5) able to speak and understand English. We will recruit 8 cohorts of 24-26 WEH and each cohort will be divided into 2 groups. Cohorts of participants will be randomized to an adapted MSC course or TAU prior to enrollment of the first participant and randomization will occur at the level of the cohort rather than the participant. This is to minimized contamination in cohorts as women live together at the RDTS but cycle out after ~3 months. Women receiving MSC or TAU will complete psychosocial questionnaires, demographics, and a Locator Guide at baseline. Women receiving MSC will participate in weekly MSC classes for 6 weeks, followed by a post-intervention follow-up and 4-month follow-up. Women receiving TAU will complete short psychological surveys each week for 6-weeks, followed by a 6-week post-baseline and 4-month follow-up.

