### **Subsection 2.2 - Phase II Scope of Work & Participant Flow Diagram**

#### 1. General Recruitment

- a. We will recruit ~8 cohorts of 24-26 WEH from Prototypes, a HealthRIGHT 360 RDTS. The RDTS staff will assist the PI and GSRs in providing a minimum of two informational meetings (advertised through flyers and verbally by staff) for interested women where they will be informed about the opportunity.
- b. [name], GSRs, or RAs will administer an eligibility screener to participants using an iPad and will collect the data using REDCap.
  - i. Key inclusion criteria are subthreshold or threshold PTSD as measured by the PCL-5 PTSD screener and no cognitive impairment as measured by the Short-Blessed Test.
- c. All participants who complete the screener will receive \$5.
  - i. Note: those who complete the screener must complete the consent to screen, but are not assigned a participant ID at this time as they have not completed the Informed Consent. As such, it is imperative that accurate information be obtained with respect to the individual's name as that will be used to link it to their subsequent data. This will be stored on REDCap on the UCLA secured server and never anywhere else.
- d. Eligible WEH who wish to participate will be invited back within the next week for enrollment and baseline assessments. The research team will review the informed consent with the potential participant and provide a copy for them to take for review. Potential participants will be given 24 hours to review the document before enrolling in the study and completing baseline measures; participants are free to waive this waiting period at their own discretion.

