### 2. Group Assignment and Intervention Procedure

a. Cohorts of participants will be randomized to an adapted MSC course or TAU prior to enrollment of the first participant. Consistent with the cluster design, randomization will occur at the level of the cohort rather than the participant. This design was chosen to avoid contamination within the cohorts, since participants

reside at the same RDTS. There will be eight cohorts in total, each with two intervention groups of 12-14 WEH. Each cohort will receive the same intervention (e.g., in Cohort 1 there will be two groups of MSC, in Cohort 2 there will be two groups of TAU). See **Table 2** below:

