The RA or GSR will then administer the eligibility screener to participants via iPad. The screener will first assess age, prior homelessness, and cognitive impairment. Cognitive impairment will be determined by a score greater than 9 on the Short Blessed Test. The screener then screens for PTSD using the PTSD Checklist for DSM-5 (PCL-5) for the worst event in their life. We will assess PTSD to their most recent event (in the past year) during the baseline and follow-up assessments. The standard PCL-5 initially starts with the identification of the presence of exposure to a DSM-5 traumatic event and then assesses whether it involved actual or threatened death, serious injury or sexual violence. The RA may need to prompt the potential participant with examples to keep them on track and to ensure that the participant is responding to an actual DSM-5 traumatic event. The next 20 items on the PCL-5 assess all four B-E PTSD criterion (re-experiencing, avoidance, negative thoughts or cognitions, hyperarousal), assessed on a Likert-type scale 0 "not at all", 1 "a little bit", 2 "moderately", 3 "quite a bit", 4 "extremely". Subthreshold PTSD will be defined as endorsing "moderately" or more to at least 2 B-E criteria; probable-PTSD will be measured by meeting criteria A-G for PTSD.

**Data collection method:** All data will be collected via iPads using REDCap and will be immediately transferred to UCLA's secure server.

All participants who complete the screener will receive \$5. It is very important to compensate all individuals who participate in the screening, even if they are not eligible!!!

Subsection 2.5 - Phase II Eligibility Criteria

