#### **Inclusion Criteria:**

- 1) Unhoused women or individual who identifies as a woman (N=202; 101 in each group)
  - a. Women over 18 years of age
  - b. Able to speak English
  - c. Experienced homelessness in the last 6 months: a homeless person is defined as anyone who spent the previous night in a public or private shelter, or on the street.
  - e. Likely subthreshold or threshold PTSD, as measured by the PCL-5.
  - f. No cognitive impairment according to a score of < 10 on the Short-Blessed Test

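### The PTSD entry rule is stated in conflicting ways (a PCL-5 total of 31 or more, or a subthreshold definition that a total of 4 can meet), and no primary PCL-5 score, metric or fixed index event is named

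*Combined protocol and SAP*

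**What the plan says.** **Entry.** The inclusion criteria in Subsection 2.1 require "probable PTSD as judged by the PCL-5 (score of 31 or higher, indicated as having optimal signal detection"). Subsection 2.2 (General Recruitment) says "Key inclusion criteria are subthreshold or threshold PTSD as measured by the PCL-5 PTSD screener", and the formal list in Subsection 2.5 says "Likely subthreshold or threshold PTSD, as measured by the PCL-5"; neither gives a score. Subsection 2.4 defines subthreshold PTSD as endorsing at the level of moderately (2 points) "or more to at least 2 B-E criteria; probable-PTSD will be measured by meeting criteria A-G for PTSD". Probable PTSD is therefore a total of 31 or more in one place and a criteria rule in another. Threshold PTSD is not defined.

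**Event.** At screening, "The screener then screens for PTSD using the PTSD Checklist for DSM-5 (PCL-5) for the worst event in their life". The next sentence of Subsection 2.4 reads "We will assess PTSD to their most recent event (in the past year) during the baseline and follow-up assessments". Subsection 2.7 instead has the worst lifetime event plus, where there is one, the worst event of the past year.

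**Outcome.** Subsections 2.7 and 2.10 list the lifetime and past-year PCL-5 together under primary outcomes. Subsection 2.7 scores the PCL-5 both continuously and by diagnostic criteria, and adds responder definitions of 5 and 10 points. The Section 3 analysis plan computes both responder measures at both follow-ups, applies a modified Poisson model to reductions in PTSD, and also fits a Gaussian model to the continuous score.

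**The concern.** Screening staff cannot apply these rules consistently. A woman with a total of, say, 22 who meets two symptom criteria is ineligible under Subsection 2.1 and eligible under Subsection 2.5. The allocation sequence makes this more than an editorial matter: "Cohorts of participants will be randomized to an adapted MSC course or TAU prior to enrollment of the first participant", the trial is open-label, and nothing says that screening staff are unaware of the arm. An ambiguous rule could be applied differently by arm, although the documents do not show that it would be.

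On the outcome side, a PCL-5 total refers to a particular event. If the event changes between visits, the change score mixes change in symptoms with change of event. A past-year score does not exist for women with no such event, and the entry rule sets no floor on it, because screening rates the lifetime event. With several scores and metrics listed and none given priority, the primary PTSD result can be chosen after the data are seen.

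**Working it through.** **1. Lowest and highest totals under each entry rule**

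Inputs: 20 items scored 0-4, with moderately = 2 (Subsection 2.4). Items per criterion, counted from the DSM-5 list in Subsection 1B.1: B 5, C 2, D 7, E 6. Symptoms required: "at least one re-experiencing symptom, one avoidance symptom, two arousal and reactivity symptoms and two cognition and mood symptoms", that is B 1, C 1, D 2, E 2.

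| Rule | Arithmetic | Limit |
|---|---|---|
| Subsection 2.1 | stated | minimum 31 |
| Subthreshold (B and C met) | 2 items × 2 | minimum 4 |
| All of B-E met | (1+1+2+2) × 2 | minimum 12 |

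The 4 also holds if one item is enough to meet any criterion. The 20 items cover B-E only, and Subsection 2.4 gives no source for criteria F and G.

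The reverse case depends on what threshold means. If it means criteria A-G, a woman who meets only one criterion fails Subsection 2.5. The highest total she can have is:

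- only D met: D 7×4 = 28, B 5×1 = 5, C 2×1 = 2, E 4 + 5×1 = 9; total 44
- only B met 41, only C met 32, only E met 41

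If one item is enough to meet a criterion, the D-only maximum is 28 + 13 = 41. So some profiles scoring 31-44 pass Subsection 2.1 and fail Subsection 2.5, and the rules are not nested. If threshold means 31 or more, Subsection 2.5 simply contains Subsection 2.1.

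**2. Index event**

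| Place | Event |
|---|---|
| Subsection 2.4, screening | worst in life |
| Subsection 2.4, baseline and follow-up | most recent, past year |
| Subsection 2.7 | worst lifetime and, if any, worst past-year |
| Subsection 2.10, post-assessment | lifetime and past-year, unspecified |

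Even if the second row only adds an assessment, most recent and worst differ. If the past year is counted back from each visit, 6/52 = 12% of the baseline window has dropped out at 6 weeks and 4/12 = 33% at 4 months, replaced by new time in which an event can occur. The documents do not say whether the window moves.

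**3. Cost of the open choice**

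Candidate results at one visit: 2 scores × 4 metrics (continuous, 5-point response, 10-point response, diagnostic) = 8. If all were independent, the chance of at least one p<0.05 under no effect would be 1 − 0.95^8 = 34%. They are correlated, so this was simulated.

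Assumptions: 81 women per arm (162/2, Section 3); correlation between the two scores 0.3/0.6/0.9 and between visits 0.4/0.6/0.8; SD 10/15/20; baseline mean 40/50; mean fall 5/10. This gives 108 scenarios of 2,000 runs. Women are independent, all have both scores, and the diagnostic metric is approximated by a total of 31 or more at follow-up. Tests are a t-test on change and a two-proportion z-test on binary metrics.

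| Choice left open | At least one p<0.05 | Median |
|---|---|---|
| 8 results | 20.1% to 28.5% | 24.4% |
| 4 metrics, score fixed | 11.7% to 16.5% | 14.1% |
| One named result | 5% | – |

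Repeat runs agree within simulation error (19% to 29% for eight results).

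**The case against.** The textual conflicts are hard to dispute; the objections go to scope and size.

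- *The simulated error rate is not that of the planned analysis.* Section 3 plans a mixed model over three time points with cohort as a random effect, and every mean, SD and correlation above is assumed. This stands: the percentages are illustrative.
- *Four metrics may be too many.* Diagnostic scoring is described in Subsection 2.7 but not clearly in Section 3, where the Poisson model may refer to the responder measures. Without the diagnostic proxy, six results give 13% to 22% (median 18%), and three on one score give 8% to 13% (median 10%). The excess shrinks but stays above 5%.
- *The lifetime score is the natural primary.* It is the only one defined for every woman, and it matches screening. That is a good reason to choose it, but Subsections 2.7 and 2.10 list both scores under primary outcomes.
- *New events are recorded.* Negative life events are updated at post-assessment and again at 4 months, and trauma exposure is examined as a covariate. This allows a change of event to be explored; it does not hold the rated event fixed.
- *The 31-44 case and the moving window are conditional.* Both are, and they are stated so here. The conclusion does not need either.

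**Conclusion.** The concern holds and must be settled before data are seen. The entry rules have floors of 4 and 31 on a 0-80 scale, and probable PTSD itself has two definitions with floors of 12 and 31. These follow directly from the text; they are logical limits, not typical scores. How many women are affected cannot be computed, because the documents give no PCL-5 distribution.

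The absence of a named primary score and metric, and of a fixed index event, is also a matter of reading. In Section 3 the word *first* gives the order of analysis, not priority, and the reference to multiple tests in the power paragraph only supports the assumed effect size. Only the size of the resulting error inflation rests on the simulation assumptions above.

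**What to change.** **Entry.** Reconcile Subsections 2.1, 2.2, 2.4 and 2.5 to one rule of the sponsor's choosing. Give one definition each of threshold and probable PTSD, with a stated source for criteria F and G if A-G is used. State which rule the 82% eligibility rate refers to, since the screening target depends on it (202/0.82 = 246.3, stated as 246).

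**Outcome, whichever entry rule is kept.** In Subsections 2.4, 2.7 and 2.10 and in Section 3, name one primary PCL-5 score and one primary metric. Tie the score to a single index event, stored in REDCap and re-used at baseline, post-intervention and 4 months. The worst lifetime event is one option: it is already collected and matches screening. If a past-year event is chosen, settle most recent against worst, fix the event at baseline, and state how women without one are handled. For the metric, the continuous analysis is already planned. Report the other score and the remaining metrics as secondary.

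**Cost.** Protocol and SAP wording plus one stored field; no new instrument, visit or sample size. Carrying the event forward from screening would rely on linkage by name, because no participant ID exists then (Subsection 2.2). Recording it at baseline avoids that.
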